Inclusion Criteria: Adults aged ≥ 45 years who have a confirmed clinical diagnosis of stroke (ischemic or hemorrhagic) according to WHO criteria [17]. Eligible patients must be 1 to 12 months post-stroke (stroke onset between 1 month and 1 year before enrollment), and be medically stable enough to participate in outpatient rehabilitation activities. Participants should have sufficient cognitive capacity and communication ability to engage in interviews and therapy sessions, and be willing to provide informed consent. They must be capable of taking part in the intervention protocols, including attending counseling sessions and performing exercises (with assistance from caregivers if needed).

Exclusion Criteria: Patients with a history of serious mental illness prior to stroke (e.g. major depressive disorder, anxiety disorder, schizophrenia, or other psychiatric illnesses diagnosed before the stroke) are excluded to avoid confounding pre-existing conditions. We also exclude those with other significant neurological disorders unrelated to stroke (e.g. Parkinson's disease, dementia) or those who experienced only transient ischemic attacks. Patients with unstable medical conditions that would interfere with participation (such as severe consciousness

disorders, uncontrolled comorbid illness, or inability to communicate) are excluded. Finally, patients who are unable to provide informed consent (for example, due to severe cognitive impairment with no available legally acceptable representative) are not enrolled.

Description of Interventions

Intervention Group: Motivational Interviewing + Home-Based Rehabilitation

Participants randomized to the intervention group receive **Motivational Interviewing (MI) therapy** in conjunction with a structured **home-based rehabilitation exercise program**, in addition to standard post-stroke care.

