(e.g. left orbitofrontal cortex, ventrolateral PFC) and how these values change from pre- to post-intervention. Prior studies suggest that greater increases in prefrontal HbO₂ activation correspond to better emotional and cognitive outcomes [26]. We will explore whether our intervention group shows increased HbO₂ responses over time relative to controls, and whether certain threshold values of HbO₂ change can distinguish participants with resolved depression from those with persistent depression by 6 months. These **fNIRS measurements** are considered an exploratory outcome and will not be used as primary endpoints, but rather to supplement and biologically contextualize the clinical findings.

All outcome instruments (questionnaires and cognitive tests) are administered in the Vietnamese language by research staff. Standardized, validated Vietnamese versions are used for all scales (e.g. the PHQ-9 and MMSE have validated translations). For quality control, the same instruments are used at each follow-up, and staff members were trained to maintain consistency in administration.

Schedule of Events (Study Timeline)

The schedule of enrollment, interventions, and assessments is based on SPIRIT guidelines and is summarized below:

- **Screening & Baseline (Month 0):** Potential participants are screened against inclusion/exclusion criteria and provide written informed consent. At enrollment (pre-intervention baseline), we collect demographic information and stroke history (including stroke type, time since onset, lesion location, disability status by Modified Rankin Scale, etc.). Baseline assessments include the PHQ-9, FSS, MMSE, Barthel Index, and SIS administered via interview, as well as the first fNIRS measurement during a cognitive task. After baseline assessments, participants are randomized to either the intervention or control group. For those in the intervention arm, the first MI session typically occurs immediately or within a week after randomization, and the home-based rehab program is initiated with a visit scheduling within the first week.

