### 4.2 Baseline Comparisons and Participant Flow

We will construct a CONSORT flow diagram to document participant flow (screened, randomized, completed, lost to follow-up) by group. Baseline demographic and clinical variables (age, sex, stroke type, time since stroke, baseline PHQ-9, etc.) will be presented by group to check for any notable imbalances. Although randomization should create comparable groups, if any substantial differences are apparent (e.g., a significant age difference or stroke severity difference between groups), these variables may be considered for inclusion as covariates in sensitivity analyses of outcomes. Categorical baseline differences will be assessed with chi-square tests and continuous differences with t-tests or Wilcoxon rank-sum tests (nonparametric) as appropriate. These tests are exploratory and will not affect the primary analysis model unless a clear need for adjustment is identified.

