### 4.3 Primary Outcome Analysis

#### *Longitudinal Analysis (Main Approach):*

We will utilize **repeated measures analysis** to assess treatment effects on the continuous primary outcomes (PHQ-9, FSS, MMSE, BI) over time. A linear mixed-effects model (LMM) will be fitted for each outcome with fixed effects for treatment group (intervention vs control), time (categorical: baseline, 1m, 3m, 6m), and the group  $\times$  time interaction. Each model will include a random intercept for each participant to account for within-subject correlations over time (assuming an unstructured covariance or other appropriate structure based on model fit). The primary parameter of interest is the group  $\times$  time interaction term at 6 months, which tests whether the change from baseline to 6 months differs between groups. If this interaction is significant ( $p < 0.05$ ), it indicates a differential treatment effect over time. We will report the estimated mean change from baseline to 6 months in each group and the difference in change between groups (with 95% CI and p-value). For reference, we will also report group differences at intermediate time points (1 and 3 months) from the same model, though these are secondary.

Assumptions of the LMM (normality of residuals, etc.) will be checked. If necessary (e.g., for skewed distributions like FSS), we may apply transformations (e.g., log transform) or use a nonparametric approach. However, given our sample size, the LMM with robust standard errors should be adequate even if mild deviations exist.

As an alternative verification, we may perform a **GEE analysis** for each outcome. The GEE will treat time as a repeated factor and use an exchangeable working correlation to account for repeated measures. GEE provides population-averaged estimates and is robust to misspecification of correlation. The results from GEE (in terms of intervention effect over time) will be compared to the LMM results. We anticipate they should converge, but any discrepancies will be examined (e.g., if dropout patterns influence results differently).

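### Time since stroke (1 to 12 months at entry) is collected but has no pre-specified place in the primary model; fixing it in advance, with a visit interaction, is a nearly free gain in precision and closes an open modelling choice

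*Protocol*

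**What the plan says.** - **Entry window.** Protocol, Eligibility Criteria: "Eligible patients must be 1 to 12 months post-stroke (stroke onset between 1 month and 1 year before enrollment".
- **Data collected.** Protocol, Schedule of Events, baseline visit: "we collect demographic information and stroke history (including stroke type, time since onset, lesion location".
- **Randomisation.** The protocol describes a computer-generated 1:1 sequence in sealed envelopes. It mentions no stratification.
- **Primary model.** SAP 4.3 specifies "fixed effects for treatment group (intervention vs control), time (categorical: baseline, 1m, 3m, 6m), and the group" by time interaction. It adds: "Each model will include a random intercept for each participant to account for within-subject correlations over time". The parameter of interest is the interaction at 6 months, "which tests whether the change from baseline to 6 months differs between groups". No baseline covariate is listed.
- **Supportive ANCOVA.** SAP 4.3 adjusts the 6-month score for the baseline value of the same outcome and nothing else.
- **Rule on imbalance.** SAP 4.2 does name the variable: "Baseline demographic and clinical variables (age, sex, stroke type, time since stroke, baseline PHQ-9, etc.) will be presented by group". If substantial differences appear, "these variables may be considered for inclusion as covariates in sensitivity analyses of outcomes". The section closes by leaving the primary model as it is unless a clear need to adjust is found. Neither a substantial difference nor a clear need is defined.
- **Subgroups.** The exploratory subgroups in SAP 4.4 are gender, age group and baseline PHQ-9. Time since stroke is not among them.

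**The concern.** The 6-month observation window covers months 1 to 7 after stroke for a patient who enters at one month, and months 12 to 18 for one who enters at a year. All four primary outcomes (PHQ-9, FSS, MMSE, Barthel Index) are analysed as change over that window. If the amount of change depends on how recent the stroke was, that part of the variation sits in the residual of the primary comparison, and a chance difference between arms in time since stroke moves the estimate in the trial at hand.

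Two things are at stake. The first is precision that could be had from a variable already on the case report form. The second is that the choice between an adjusted and an unadjusted primary model waits on a look at the baseline data, in a SAP whose introduction says it was finalised early to prevent data-driven decisions.

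**Working it through.** **Inputs from the protocol (Sample Size and Justification):** difference 3.43 PHQ-9 points, SD of change 5.5, two-sided alpha 0.05, power 0.80, 43 per group required, 46 per group enrolled.

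**Input not in the documents:** R², the share of within-arm variance in 6-month change explained by time since stroke. It is assumed, over the range 0 to 20%.

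**Step 1. The plan's own figure.** n per group = 2 × (1.960 + 0.842)² × 5.5² / 3.43² = 40.4, so 41; by the noncentral t distribution, 42. The stated 43 is within two patients of this. Unadjusted power (t-based) is 81.6% at 43 per arm and 84.1% at 46, above the 80% target.

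**Step 2. What adjustment would gain.** Adjustment replaces the SD by 5.5 × √(1 − R²). The SE at 46 per arm is that SD × √(2/46). Power is t-based.

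| Assumed R² | SD | SE at 46 per arm | Power, 43 per arm | Power, 46 per arm |
|---|---|---|---|---|
| 0% | 5.50 | 1.15 | 81.6% | 84.1% |
| 1% | 5.47 | 1.14 | 81.9% | 84.5% |
| 5% | 5.36 | 1.12 | 83.5% | 85.9% |
| 10% | 5.22 | 1.09 | 85.4% | 87.7% |
| 20% | 4.92 | 1.03 | 89.2% | 91.1% |

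The equivalent gain in sample size is 1/(1 − R²): 1.05 at 5%, 1.25 at 20%.

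**Step 3. Overall validity without adjustment.** In 20,000 simulated trials with 46 per arm and entry times uniform over 1 to 12 months (an assumption), the unadjusted test had type I error of 5.1% at correlations of 0, 0.3 and 0.5 between time since stroke and change. Its mean estimate stayed within 0.01 of the true −3.43. At a correlation of 0.3 (R² 9%), power was 83.8% unadjusted and 86.7% adjusted.

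**Step 4. Accuracy given the observed imbalance.** With uniform entry, the SD of time since stroke is 11/√12 = 3.18 months, and 95% of randomisations give an arm difference within 1.96 × 3.18 × √(2/46) = 1.3 months. At an imbalance of c standard errors, the unadjusted estimate shifts by c√R² of its own SE (1.15 points), and its conditional variance is (1 − R²) times the nominal one. Conditional two-sided error:

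| Imbalance c | R² 5% | R² 10% | R² 20% |
|---|---|---|---|
| 0 | 4.4% | 3.9% | 2.8% |
| 0.67 (median) | 4.7% | 4.4% | 3.8% |
| 1 | 5.0% | 5.0% | 4.9% |
| 1.96 | 6.6% | 8.2% | 11.4% |

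At c = 1.96 the PHQ-9 shift is 0.50, 0.71 and 1.01 points. An imbalance of at most 1 SE occurs in about 68% of randomisations, and there the conditional error is at or below 5%.

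**Step 5. How the covariate must enter.** Write T for time since stroke. A main effect γT appears in both the baseline and the 6-month score, so it drops out of their difference. A term that varies by visit, δ₆T, stays in the 6-month change. In one simulated complete data set, the group by 6-month estimate was −0.792 with no covariate, −0.792 with T as a main effect, and −1.436 with T by visit.

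**The case against.** The strongest reply is that nothing here is an error. A reader might infer that natural recovery biases the treatment effect. The documents do not support that: a concurrent randomised control arm goes through the same recovery, a chance imbalance is as likely to hide an effect as to create one, and the unadjusted SE already allows for it (Step 3). The conditional error of 6.6 to 11.4% is a tail case, since an imbalance of 1.96 SE is exceeded in only 5% of randomisations.

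A reader might also infer that the SAP shuts time since stroke out of the primary analysis. It does not. SAP 4.2 lists the variable, allows it in sensitivity analyses, and leaves the primary model open to change if a clear need is found. The group by time contrast also removes any effect of time since stroke on the level of the outcome; only its effect on change remains.

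Finally, no R² can be derived from the documents, for PHQ-9 or for the other three scales. It may be near zero, and the SD of 5.5 may already contain this heterogeneity.

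All of this stands. It limits the point to an improvement. It does not rescue the rule in SAP 4.2, which is optional, triggered by observed data and without a threshold. Nor does that rule say that the covariate must interact with visit, so a team that added it as an ordinary covariate would report an adjusted model with the same primary estimate.

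**Conclusion.** The point holds as a free improvement and not as a flaw in validity. The plan collects a plausible predictor of change, spreads it over an 11-month entry window, and leaves its use to an undefined judgement after baseline data are seen. The unadjusted comparison remains unbiased, keeps 5% overall type I error and meets its power target, so it would be wrong to conclude that the trial is underpowered or its effect confounded on this account.

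The gain at 46 per arm runs from nothing at R² of 0 to 7 percentage points of PHQ-9 power at R² of 20% (84.1% to 91.1%). These figures rest on the protocol's difference and SD, complete data, a linear relation and an assumed R². The imbalance in months also assumes uniform entry times. Power was worked out only for PHQ-9, because the protocol gives no effect size or SD for the other three outcomes.

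**What to change.** - **SAP 4.3, primary model.** Pre-specify time since stroke at enrolment as a continuous covariate (for example log months), with its interaction with visit, for all four outcomes and whatever the observed balance.
- **SAP 4.3, ANCOVA.** Add time since stroke beside the baseline score.
- **SAP 4.2.** Take time since stroke out of the imbalance-triggered rule. It can still be shown in the baseline table.
- **If the primary analysis has already been run.** Leave it as it is and report the adjusted model as a labelled sensitivity analysis for all four outcomes.

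The cost is one sentence in the SAP and about four fixed-effect parameters per model (one main effect and three follow-up visit interactions). No patients, visits or data items are added. If R² is near zero, there is little or no gain and a negligible loss of degrees of freedom.

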In addition, traditional neuroimaging methods to monitor mental health recovery (e.g. fMRI, PET, EEG) are often impractical in routine care due to cost and limited portability [11-13]. Functional Near-Infrared Spectroscopy (fNIRS) offers a noninvasive, portable, and low-cost brain monitoring tool that can track changes in cerebral blood oxygenation with high temporal resolution [14]. fNIRS has been used successfully to evaluate depression and other mental health conditions by detecting hemodynamic changes in the prefrontal cortex [15, 16]. Applying fNIRS in post-stroke patients could provide an objective biomarker of improvement in depression and cognitive function in response to our intervention [15]. This study is pioneering in Vietnam as it combines physical rehabilitation, MI, and fNIRS-based monitoring to address post-stroke health comprehensively. The knowledge gained may guide future stroke care programs and health policy in resource-limited settings.

Trial Objectives and Hypotheses

Primary Objective: To evaluate the effectiveness of a 6-month multifaceted intervention (Motivational Interviewing plus a home-based rehabilitation program) in improving the mental health (reducing depressive symptoms, fatigue, and cognitive impairment) and physical

functional status of post-stroke patients, compared to standard care alone. The primary endpoints include changes in depression severity, fatigue level, cognitive function, and activities of daily living from baseline to 6 months.

Secondary Objectives: (1) To assess the impact of the intervention on post-stroke quality of life. (2) To explore neurobiological changes associated with depression improvement by measuring prefrontal cortex oxyhemoglobin concentration changes using fNIRS, and determine whether fNIRS biomarkers can serve as predictors of depression status in stroke survivors.

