Hypotheses: We hypothesize that stroke survivors receiving the combined MI and home-based rehabilitation intervention will show significantly greater improvements in mental health outcomes (lower Patient Health Questionnaire-9 depression scores and Fatigue Severity Scale scores, improved Mini-Mental State Examination scores) and physical function (higher Barthel Index scores) over 6 months, compared to those receiving standard care. We also hypothesize that the intervention group will exhibit measurable increases in prefrontal cortical activation (oxyhemoglobin levels) on fNIRS correlating with reduction in depressive symptoms, and that specific fNIRS-derived metrics will predict depression remission status with reasonable accuracy.

Study Design

This study is a single-center, parallel-group randomized controlled trial with a 1:1 allocation ratio to intervention versus control. The trial was conducted at the Vietnam National Geriatric Hospital from 2021 to 2022. A total of 92 stroke survivor participants were enrolled and randomly assigned to either the Intervention group, which received a multi-component program (Motivational Interviewing plus a home-based rehabilitation regimen), or the Control group, which received standard care and general health advice. The study duration for each participant is approximately 6 months, with assessments at baseline and follow-up at 1, 3, and 6 months post-enrollment. Figure 1 presents the planned participant flow per CONSORT guidelines (see Schedule of Events below for timeline of activities). The trial is open-label: due to the nature of the interventions, neither participants nor intervention providers were blinded to group assignment. To reduce potential bias, outcome assessments were standardized, and the data analyst/statistician remained blinded to group labels during analysis.

Eligibility Criteria

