These four measures (PHQ-9, FSS, MMSE, and Barthel Index) are considered the primary outcomes, representing mental and physical health domains targeted by the intervention. In addition, we track a secondary outcome of overall post-stroke recovery:

- **Quality of Life:** Evaluated using the **Stroke Impact Scale 3.0 (SIS-16)**, a stroke-specific quality-of-life questionnaire [24]. The SIS assesses 8 domains including strength, hand function, mobility, ADL/IADL, memory, communication, emotion, and social participation. Domain scores and an overall composite can be calculated on a 0–100 scale, with higher scores indicating better functioning and quality of life [24]. We will primarily use the total SIS score as an outcome of global recovery. (This measure is secondary/exploratory; not all participants may complete the full SIS due to time constraints.)
- **Neuroimaging Biomarkers (Exploratory):** Changes in cerebral oxyhemoglobin concentration in the prefrontal cortex, as measured by fNIRS, serve as an exploratory biomarker of depression and cognitive improvement. A portable 48-channel fNIRS device (NIRSIT, OBELAB, South Korea) is used to record cortical hemodynamic responses while participants perform a brief cognitive task (e.g. verbal fluency task) at baseline, 3 months, and 6 months (fNIRS is not administered at the 1-month visit). The fNIRS optode array is positioned over the forehead (frontopolar and lateral prefrontal regions) to capture activity in brain areas implicated in mood regulation (such as the orbitofrontal cortex). Oxyhemoglobin (HbO_2) and deoxyhemoglobin signals are calculated using the modified Beer–Lambert law and are sampled at high temporal resolution during the cognitive challenge [25]. For analysis, we will examine the mean change in HbO_2 from baseline during task performance for specific regions of interest

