- **6-Month Follow-up (Month 6, end of study):** At the end of the 6-month study period, all participants undergo the final evaluation. The same battery of outcome measures (PHQ-9, FSS, MMSE, Barthel Index, SIS) is administered, and the **final fNIRS** measurement is conducted. The 6-month outcomes represent the primary endpoint for evaluating intervention effectiveness. By this time, the intervention group has concluded all activities (the last home visit by the physical therapist typically occurs around month 5 or 6 with the monthly schedule). We document any post-study referrals or ongoing care plans for both groups. After completing the 6-month assessment, participants are thanked and exit the study. Those in the control group are offered an opportunity to receive the intervention program after study completion, if appropriate, as an ethical consideration.

Sample Size and Justification

The sample size was determined based on detecting a clinically meaningful difference in depression outcomes between the two groups at 6 months. Using a two-sample comparison of mean change in PHQ-9 scores (intervention vs control), we assumed a difference in mean PHQ-9 reduction of approximately 3.43 points with a standard deviation of about 5.5, based on prior research on post-stroke depression interventions [27]. With a two-sided $\alpha=0.05$ and power (1– β) of 0.80, the estimated minimum sample required was 43 patients per group (calculated via the formula for comparing two means). We planned to enroll 46 patients in each group (total N=92) to account for potential drop-outs and ensure adequate power. This sample size also offers >80% power to detect medium-to-large effects on secondary continuous outcomes like FSS and Barthel Index, given similar variance assumptions. The actual achieved sample size was 92, which meets these targets. No interim analyses for efficacy were planned (due to the relatively short intervention duration and moderate sample size), so the full sample contributes to the final analysis.

Randomization, Allocation Concealment, and Blinding

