## 1. Introduction and Study Overview

This Statistical Analysis Plan (SAP) describes in detail the planned analytical approaches for the above-mentioned randomized controlled trial. The study's objective is to evaluate the efficacy of a 6-month intervention combining Motivational Interviewing (MI) and a home-based rehabilitation program versus standard care in improving post-stroke outcomes. A total of 92 stroke patients were randomized (1:1) to the intervention or control group. Outcomes are measured at baseline, 1 month, 3 months, and 6 months post-intervention. The primary outcomes include depression (PHQ-9 score), fatigue (FSS score), cognitive function (MMSE score), and physical function (Barthel Index). Secondary outcomes include quality of life (Stroke Impact Scale) and exploratory fNIRS-based biomarkers of cortical activity. No interim analyses were conducted; all analyses described here are post-finalization of data collection. This SAP is finalized prior to unlocking the database to avoid data-driven decisions.

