### 3. Outcomes and Endpoint Definitions

#### Primary Efficacy Outcomes:

- **Depression Severity:** Change in Patient Health Questionnaire-9 (PHQ-9) score from baseline to follow-ups. The PHQ-9 is a 9-item scale (0–27 range); higher scores indicate worse depressive symptoms. The primary comparison will be the difference in mean PHQ-9 change from baseline to 6 months between groups. Additionally, trajectories over all time points will be considered. We will also examine the proportion of participants in each group achieving remission of depression (PHQ-9 < 5, for example) at 6 months as a supportive outcome.

- **Fatigue Level:** Change in Fatigue Severity Scale (FSS) score (range 9–63, higher = more fatigue). Same approach as PHQ-9: continuous score change and possibly categorization (e.g., FSS  $\geq 36$  indicating significant fatigue) for supplementary analysis.

- **Cognitive Function:** Change in Mini-Mental State Examination (MMSE) score (0–30, higher = better cognitive function). We will consider the mean change and group differences; additionally, the proportion of participants with cognitive impairment (MMSE  $\leq 24$ ) at each time point will be noted.

- **Physical Functional Independence:** Change in Barthel Index (BI) score (0–100, higher = more independent). Primary focus on mean score change at 6 months. Also, we may categorize outcomes (e.g., BI  $\geq 90$  as independent vs <90) for descriptive comparison.

Each of these primary outcomes will be analyzed as a continuous variable using appropriate parametric or nonparametric methods as outlined in Section 4. The primary time horizon for efficacy is the 6-month post-intervention assessment, though intermediate time points will be analyzed to observe trends.

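### The protocol's sample-size section calls fatigue and Barthel secondary although they are primary, and its claim of more than 80% power for medium-to-large effects holds only from d of about 0.59

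*Protocol*

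**What the plan says.** The protocol's Sample Size and Justification section rests on one scale: "The sample size was determined based on detecting a clinically meaningful difference in depression outcomes". It assumes a difference of 3.43 points in mean PHQ-9 reduction, an SD of about 5.5, two-sided alpha 0.05 and power 0.80. From these it derives 43 per group, and it enrols 46 per group. It then extends the result to other scales: "This sample size also offers >80% power to detect medium-to-large effects on secondary continuous outcomes like FSS and Barthel Index", with the qualifier "given similar variance assumptions". It gives no effect size and no SD for those scales, and it does not name MMSE.

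Elsewhere the standing of the four scales is different. Trial Objectives and Hypotheses: "The primary endpoints include changes in depression severity, fatigue level, cognitive function, and activities of daily living from baseline to 6 months". Outcome Measures: "These four measures (PHQ-9, FSS, MMSE, and Barthel Index) are considered the primary outcomes". SAP Section 1 lists the same four scales as primary. SAP Section 3 describes each of them under its primary efficacy heading and adds: "Each of these primary outcomes will be analyzed as a continuous variable".

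SAP Section 4.3 (Effect Size) defines Cohen's d as the difference in mean change over the pooled SD of change, and takes about 0.5 as medium and 0.8 as large.

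**The concern.** The sample-size section disagrees with four other places on whether FSS and Barthel are primary. Someone who reads only that section would take the trial to have one primary outcome and would give the fatigue and function results less weight than the rest of the plan does.

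The power sentence matters for a related reason. It is the only statement in either document on what the trial can detect on scales other than PHQ-9. If medium-to-large is read as starting at the SAP's medium benchmark, the sentence promises at least 80% power at d = 0.5. A true effect of that size would in fact be missed about one time in three by the comparison the section describes. A null result on FSS, MMSE or Barthel could then be taken as firmer evidence of no medium effect than it is.

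**Working it through.** **Inputs.** From the protocol's sample-size section: difference 3.43, SD 5.5, two-sided alpha 0.05, power 0.80, 43 per group required, 46 per group enrolled. From SAP Section 4.3: d on the SD of change, medium 0.5, large 0.8.

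**Step 1: the plan's own figure.** Design effect: d = 3.43/5.5 = 0.624. Normal formula: n per group = 2 × [(1.960 + 0.842) × 5.5/3.43]² = 40.4, so 41. The t-based solution is 41.3, so 42. The stated 43 is within two patients of both and slightly on the safe side, so the PHQ-9 calculation reproduces.

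**Step 2: power of one comparison.** With n per arm, the two-sample t statistic has 2n − 2 degrees of freedom and noncentrality d × √(n/2). At d = 0.5 the noncentrality is 0.5 × √23 = 2.398 for n = 46, and 0.5 × √21.5 = 2.318 for n = 43. The two-sided 0.05 critical values are 1.987 and 1.989. The noncentral t distribution gives:

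| True d (SD of change) | 46 per arm | 43 per arm |
|---|---|---|
| 0.5 (SAP medium) | 66.0% | 63.0% |
| 0.624 (PHQ-9 design effect) | 84.1% | 81.6% |
| 0.65 (midway between 0.5 and 0.8) | 87.0% | 84.6% |
| 0.8 (SAP large) | 96.7% | 95.6% |

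The 46 column assumes that everyone is analysed. The 43 column is the plan's stated minimum.

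**Step 3: smallest d with 80% power.** Solving the same equation for d gives 0.590 with 46 per arm and 0.611 with 43. The normal approximation gives 0.584 and 0.604.

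**Step 4: sample needed at d = 0.5.** The t-based solution is 63.8, so 64 per arm.

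**Step 5: what baseline adjustment could add.** SAP Section 4.3 also plans a supportive ANCOVA of the 6-month score on baseline. With equal variances at the two times and correlation r between baseline and 6 months, the SD of change is σ√(2(1 − r)) and the ANCOVA residual SD is σ√(1 − r²). A d of 0.5 on the SD of change therefore becomes 0.5 × √(2/(1 + r)). The documents give no r, so a range is assumed:

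| Assumed r | Effective d | 46 per arm | 43 per arm |
|---|---|---|---|
| 0.3 | 0.620 | 84% | 81% |
| 0.5 | 0.577 | 78% | 75% |
| 0.7 | 0.542 | 73% | 70% |

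**The case against.** The best defence is that medium-to-large does not mean medium. The section's own design effect, 0.624, lies between the two benchmarks, and its remark on similar variances can be read as carrying that effect over to the other scales. At 0.624 and at the midpoint 0.65 the claim is true. The benchmarks in SAP Section 4.3 were also set for interpreting observed effects, not for planning. This stands in part: the sentence holds over most of the range from 0.5 to 0.8. It fails between 0.5 and about 0.59, and because the section gives no d, the reader cannot tell that this part is not covered. The remark on variances does not close the gap, because d is already standardised.

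A second defence is that 66% belongs to the unadjusted comparison, and that the supportive ANCOVA does better. That is correct, and the range is shown above. But the sample-size section describes a comparison of mean change, and the main mixed model in SAP Section 4.3 targets the difference in change from baseline. The section claims no gain from adjustment.

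A third is that the label is one word. All four scales are analysed in the same way, the 92 participants are already enrolled, and the confidence intervals will show the precision reached. It is true that no analysis changes. The contradiction about which outcomes are primary remains.

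A reader might also go further and infer that four unadjusted primary tests leave the trial's error rate uncontrolled. SAP Section 4.7 addresses this openly: it declines adjustment, gives its reason and says that no single hypothesis decides. Its word for how many scales should be significant is loose, but that is missing detail rather than an error. Nor do the preliminary findings in SAP Section 4.5 show that between-group results on the four scales had been seen. They concern fNIRS measures, SAP Section 1 says that the plan was finalised before the database was unlocked, and the protocol keeps the analyst blinded until the primary analyses are complete.

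**Conclusion.** The point holds as a correction of wording. FSS and Barthel are mislabelled as secondary in the sample-size section, and MMSE has no named power statement. The claim of more than 80% power is true from d of about 0.59 (46 per arm) or 0.61 (43 per arm). It falls to 66% or 63% at the SAP's medium benchmark, a shortfall of 14 to 17 percentage points.

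These figures assume normally distributed change scores, equal variances, equal arms and a single two-sided 0.05 test without baseline adjustment. They do not show that the trial was wrongly sized: the PHQ-9 calculation reproduces, with 84% or 82% power at its design effect. They also do not show low power for the effects that FSS, MMSE or Barthel may really have, because the documents assume no effect for those scales.

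**What to change.** In the protocol's Sample Size and Justification section:

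1. Call FSS, MMSE and Barthel Index primary, in line with the outcome section and the SAP, and say that the trial was sized on PHQ-9 only.
2. Replace the power sentence with: *For a single unadjusted two-sided 0.05 comparison of mean change, 80% power for d of about 0.59 or more (46 per arm) or 0.61 or more (43 per arm); about 66% or 63% at d = 0.5.*
3. Add a note that the supportive baseline-adjusted ANCOVA would have more power, by an amount that depends on a baseline-to-6-month correlation not given in the plan.

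The change needs no extra participants and no new analysis. Its cost is a less favourable stated power figure.
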